9.5.7 Pharmacokinetic Analyses

The plasma PK of CORT125281, enzalutamide, and major metabolites, including M2 will be characterized using non-compartmental analysis, and analyte concentration versus time plots will be provided. PK parameters listed in Table 15 will be calculated, whenever possible, from plasma concentrations of CORT125281, enzalutamide, and M2, and combined exposure to both enzalutamide and M2.

Table 15 PK Variables for Analysis

AUC _{0-last}	Area under the plasma concentration-time curve calculated using linear trapezoidal summation from time 0 to time last, where “last” is the time of the last measurable concentration
AUC ₀₋₂₄	Area under the plasma concentration-time curve from 0 to 24 hours, calculated using linear trapezoidal summation
AUC _{0-inf}	Area under the plasma concentration-time curve from 0 to infinity, calculated using the formula: $AUC_{0-inf} = AUC_{0-last} + C_{last} / \lambda_z$, where λ_z is the apparent terminal elimination rate constant (whenever possible)
C _{max}	Maximum observed plasma concentration
C _{min,ss}	Minimum observed plasma concentration, at pre-dose at steady state
CL/F	Apparent oral clearance
T _{max}	Time of the maximum plasma concentration (obtained without interpolation)
λ_z	Terminal elimination rate constant (whenever possible)

C_{last}, last measurable concentration.

Missing dates or times may be imputed for PK samples if the missing values can be established with an acceptable level of accuracy based on other information obtained during the visit in question. If PK sampling for a given patient is not performed according to protocol instructions, the corresponding concentration data may be excluded from the PK analyses.

Concentration data and PK parameters will be tabulated and summarized using descriptive statistics. PK relationships to measures of efficacy or toxicity may also be explored. Additional PK analyses may be performed, as deemed appropriate.

The PK of CORT125281, the natural log (ln) transformed C_{max}, AUC_{0-t}, and AUC_{inf}, and other PK parameters will be analyzed by analysis of variance (ANOVA) adjusted for food effect and other potential factors that may influence the outcome. The fed state versus fasted state comparison for C_{max}, AUC_{0-t}, and AUC_{inf} will be carried out using 90% CIs for the ratios of these parameters based on the models. If the 90% CIs are contained within the limits 0.80 to 1.25, lack of substantial food effect will be inferred. The T_{max} values between the fed and fasted state will be compared using non-parametric tests.

9.6 Exploratory Analyses

Exploratory analyses will characterize PRO and QoL using the following endpoints:

- Median time to deterioration defined as ≥ 10 -point decrease from baseline on the overall FACT-P score
- Change from baseline in the overall FACT-P scores, as well as its subscales measuring physical and emotional well-being, prostate-cancer specific QoL, and pain-related score
- Percentage of patients who filled out the survey and showed improvement in FACT-P score, and its subscales

Additional exploratory analyses to evaluate the effects of CORT125281 and enzalutamide on pain and time to worsening of pain will be prespecified in the Statistical Analysis Plan.

The distribution of time to deterioration will be summarized using the Kaplan-Meier method. The change from baseline in the FACT-P score will be analyzed using paired t test. The percentage of patients who show improvement will be summarized.

Changes from baseline in PD variables will be summarized descriptively and exploratory analyses of trends with dose and time may be conducted. The baseline value is defined as the last measurement before the beginning of study treatment (CORT125281 or on-study enzalutamide, whichever is earlier) administration. The relationship between drug concentration variables and PD variables may be explored. The dependence of observations from the same patient may be appropriately taken into account in all of the above analyses.

Exploratory analyses will include assessment of the relationship of pre-treatment tumor GR expression by IHC with clinical outcome and assessment of the scoring method/threshold that is most predictive of response may be detailed separately. These analyses will include analyses of changes in GR expression assessed by IHC and will compare pre- and post-treatment to assess changes over time as potential markers of sensitivity and resistance. The relationship between drug concentration variables and blood cortisol and ACTH will be assessed, in addition to the relationship with clinical outcomes.

9.7 Subgroup Analyses

Analyses for preliminary efficacy and exploratory analyses for QoL will be done in all patients and in the following subgroups of patients, if a sufficient number of patients are evaluable in each subgroup:

- Enzalutamide and/or abiraterone naïve
- Prior treatment with abiraterone
- Enzalutamide resistant
- ARV7 positive and ARV7 negative (defined by positive on CTC and/or liquid biopsy, or most current definition at the completion of the study)
- GR positive and GR negative (defined by IHC and/or CTCs)

9.8 Data Review Committee

The DRC will consist of Investigators, the Medical Monitor, a Clinical Pharmacologist, and additional members, as appropriate. The DRC will review the safety, PK, and PD data following

the completion of each cohort during the Dose-Determination Phase Segment 1, after all patients have completed 3 cycles of treatment in Dose-Determination Phase Segment 2, and at least every 6 months during the Expansion Phase. If at any time during the Expansion Phase the DLT rate exceeds 33%, the dose will be declared non-feasible and no additional patients will be enrolled to that dose. A lower dose level may be evaluated, per the recommendation of the DRC.

9.9 Interim Safety Analyses

In Dose-Determination Segment 1, the DRC will make recommendations regarding escalation to the next planned dose, repeating a prior dose, or investigating other dose cohorts (ie, intermediate or lower doses) until the MTD/RD is identified (Section 5.4.1). If a biologically active dose is determined as defined by the dose level at which CORT125281 has been demonstrated to inhibit GR and at which the DLT rate is <33%, the Dose-Determination Phase may be completed prior to the determination of the MTD, per the recommendation of the DRC.

In Dose-Determination Phase Segment 2 (Section 5.4.2), after all patients complete 3 cycles of treatment or discontinue treatment, the data will be unblinded and the DRC will meet to review the safety and available PK and PD data. The DRC will evaluate the frequency of DLTs, the DLT rate (number of DLTs per week [7-day period] during the DLT-evaluation period), and overall tolerability to determine the feasibility of the dose titration regimen for the Phase 2 RD.

In the Expansion Phase, an interim safety analysis will be conducted after a total of 20 patients complete 3 cycles of therapy.

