enzalutamide 160 mg QD. Twelve patients have received CORT125281 in combination with enzalutamide, and 2 patients discontinued the study during the enzalutamide lead-in and did not receive CORT125281. In Cohort 1, two patients received CORT125281 180 mg BID with enzalutamide. Both patients experienced dose-limiting toxicities (DLTs), including Grade 3 fatigue (n=1), and the concurrent SAEs of Grade 3 fatigue and Grade 3 musculoskeletal pain (n=1); thus CORT125281 180 mg BID was deemed intolerable. A lower dose (CORT125281 140 mg BID) was evaluated in Cohort 2. In Cohort 2, 1 of 3 patients experienced a DLT (SAE of Grade 3 acute pancreatitis). After the third patient enrolled to Cohort 2, an interim assessment of PK and safety was conducted. Based upon the absence of a clinically significant drug interaction of CORT125281 on enzalutamide exposure, enrollment to the subsequent cohort was initiated to further evaluate the CORT125281 140 mg BID dose level without the enzalutamide lead-in. Seven patients have been enrolled to Cohort 3. One patient was not evaluable for DLTs due to disease progression during Cycle 1. Of the 6 remaining patients, no DLTs were observed and the dose was considered tolerable.

Twelve patients (100%) who have received at least 1 dose of CORT125281 in combination with enzalutamide reported greater than 1 TEAE. Five patients (42%) reported TEAEs of Grade 3 or greater considered related to CORT125281; the most frequent TEAE of Grade 3 or greater was fatigue (n=2; 17%). An alternative schedule (once daily [QD] dosing of CORT125281) is planned to optimize the biologically active dose prior to proceeding to the Phase 2 expansion cohorts.

CORT125281-602

In accordance with the study design, 6 healthy subjects received a single oral dose of [¹⁴C]-CORT125281 360 mg (6 × 60-mg capsules). No TEAEs were reported in this study.

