Once both segments of the Dose-Determination Phase are complete, and the RD has been determined, patients will be enrolled into expanded safety cohorts to further evaluate the safety, tolerability, preliminary efficacy, and PK of CORT125281 in combination with enzalutamide and exploratory biomarkers of sensitivity or resistance. Based on the hypothesis that GR activation compensates for diminished AR signaling in CRPC treated with enzalutamide and facilitates cancer cell survival; the expansion cohorts will include:

- Abiraterone (Abi)-Resistant Cohort: Patients who have previously progressed while receiving abiraterone
- AR Antagonist (ARant)-Resistant Cohort: Patients who have previously progressed while receiving enzalutamide or other second-generation AR inhibitors.

The effect of food on CORT125281 PK will be assessed in 10 patients enrolled in the Expansion Phase. The expansion cohorts will be enrolled in parallel.

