During the double-blind portion of the Dose-Determination Phase (ie, Segment 2), an unblinded Medical Monitor independent of the study team will provide additional oversight for the study, including review of serious unexpected AEs considered related to either CORT125281 or enzalutamide and DLTs.

The DLT-evaluation period will extend from the first dose of CORT125281 through the completion of Cycle 3. The DLT-Evaluable Population will include all patients in Segment 2 who received at least 1 dose of CORT125281 and fulfilled at least 1 of the following:

- Completed 3 cycles of treatment with CORT125281 + enzalutamide and received at least 75% of the study regimen
- Experience a DLT

Patients who are non-evaluable for DLTs will include the following:

- Received <75% of the study regimen for reasons other than toxicity
- Patients who withdraw from the study prior to completion of Cycle 3 for reasons other than toxicity (eg, lost to follow-up, withdrawal of consent, or disease progression)

Patients who are non-evaluable for DLTs will be allowed to continue in the study and receive CORT125281 in combination with enzalutamide. Patients who are non-evaluable for DLTs may be replaced to allow a sufficient number of patients to evaluate DLTs (Section 9.4.1).

After all patients complete 3 cycles of treatment or discontinue treatment, the data will be unblinded and the DRC will meet to review the safety and available PK and PD data. The DRC will evaluate the frequency of DLTs, the DLT rate (number of DLTs in DLT-evaluable patients per week [7-day period] during the DLT-evaluation period), and overall tolerability in their assessment of the dose titration regimen as the Phase 2 RD.

If the DLT rate for the regimen is $\geq 33\%$, alternative titration schemes may be considered as the regimen for the RD, such as greater time increments between dose escalations or limiting the upper range of the regimen to those dose levels corresponding to a DLT rate of $< 33\%$. Once the DRC has determined the RD, patients assigned to Arm B who have not experienced dose reductions due to toxicity will then escalate the CORT125281 dose per the recommended upward titration regimen.

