9.4.2 Expansion Phase

Approximately 40 patients will be enrolled in the Expansion Phase.

- Twenty patients in the Abi-Resistant Cohort will ensure at least 80% power for detecting a doubling of the background rate of 23.5% in the PSA responder, defined as $\geq 50\%$ improvement in the PSA level from baseline. This calculation assumes 1-sided 0.1 significance level exact test of a single proportion against a fixed alternative. Under these assumptions, an absolute response rate of 40%, which represents a 59% improvement over the background rate, will support further evaluation of the regimen in the clinical program.
- Twenty patients in the ARant-Resistant Cohort will ensure at least 80% power for detecting an absolute improvement of 18% in the PSA responder rate over a rate of 8%, based upon the assumption that a response rate of 8% or less indicates no benefit. This calculation assumes 1-sided 0.1 significance level exact test of a single proportion against a fixed alternative. Under these assumptions, an absolute response rate of 20%, which represents an improvement of 12% over the background rate, will support further evaluation in the clinical program.

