aPTT, activated partial thromboplastin time; CBC, complete blood count; CT, computed tomography; DRC, Data Review Committee; ECG, electrocardiogram; ECOG, Eastern Cooperative Oncology Group; EOT, End-of-Treatment; FACT-P, Functional Assessment of Cancer Therapy-Prostate; FT3, free triiodothyronine; FT4, free thyroxine; INR, international normalized ratio; LDH, lactic dehydrogenase; Mnth, month; MRI, magnetic resonance imaging; PSA, prostate-specific antigen; PRO, patient-reported outcomes; PT, prothrombin time; QoL, quality of life; TSH, thyroid-stimulating hormone; TT3, total triiodothyronine.

Note: In all parts of the study, a cycle of therapy is considered to be 28 days with no rest periods in between cycles. All procedures within a cycle should be counted by calendar day from Day 1 of that cycle. A 2-day window will be allowed for study visits.

- a. The Lead-In Period only applies to patients in Dose-Determination Phase Segment 1 and patients in the Expansion Phase Food-Effect Subcohort. Lead-in duration is 28 days in Dose-Determination Phase Segment 1, and 7 days for patients in the Expansion Phase Food-Effect Subcohort. When a recommended dose of enzalutamide is determined by the DRC, the DRC may recommend discontinuing the lead-in for subsequent cohorts.
- b. Upon discontinuation of CORT125281, if the patient continues on enzalutamide alone (Section 5.7.1.1) and all toxicities attributed to CORT125281 have resolved, visit frequency can be decreased per the Investigator's standard of care. The patient should come for their regularly scheduled visit (the subsequent cycle) after discontinuing CORT125281. After this visit, visits can be conducted less frequently per Investigator discretion, but at a minimum every 3 cycles while on enzalutamide alone; at these visits they will have the assessments listed in the "Cycle 4 & Beyond" column. After discontinuation of enzalutamide, the patient will return for their EOT Visit, and then for an EOT +30 Days Visit.
- c. Phone follow-up for overall survival (ie, the date and cause of death, and post-treatment information) will continue every 4 months until the study endpoints are met or 2 years from the date that the last patient enrolls in the study (whichever is later).

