8.11. Interim Analyses or Timing of Analyses

The DRC consisting of Investigators, the Medical Monitor, a Clinical Pharmacologist, and additional members as appropriate will review the safety, PK, and PD data following the

completion of each cohort during Dose-Determination Phase Segment 1, after all patients have completed 3 cycles of treatment in Dose-Determination Phase Segment 2, and at least every 6 months during the Expansion Phase.

An interim safety analysis will be conducted after a total of 20 patients complete 3 cycles of therapy in the Expansion Phase. If at any time during the Expansion Phase the DLT rate exceeds 33%, the dose will be declared non-feasible, and no additional patients will be enrolled to that dose. A lower dose level may be evaluated, per the recommendation of the DRC.

9. Efficacy Analyses

The recommendations of the PCWG3 will be used to determine disease response for this study. Tumor assessments include ^{99m}Tc -methylene diphosphonate radionucleotide bone scintigraphy and CT of the chest, abdomen, and pelvis. Baseline tumor assessment will be performed within 28 days before the first dose of enzalutamide (for Dose-Determination Phase Segment 1) and/or the first dose of exicorilant (for Dose-Determination Phase Segment 2 and Expansion Phase). Post-baseline tumor assessments will be performed every 8 weeks after the first dose of enzalutamide and/or exicorilant for the first 24 weeks. Thereafter, tumor assessments will occur at intervals of 12 weeks until disease progression. Objective responses will be confirmed no less than 4 weeks after the criteria for response are first met (if possible, 4 – 6 weeks). PSA, alkaline phosphatase (ALP), and lactic dehydrogenase (LDH) will be assessed at the Baseline/Screening Visit and Day 1 of each cycle. The ITT population will be used to address the secondary and exploratory efficacy objectives of the study. Disease response and progression assessed according to RECIST v1.1 by the Investigator will provide the basis for efficacy endpoints.

At all scheduled visits, data recorded for target, non-target, and new lesions, and Investigator response assessment will be presented in by-patient listings. Summary tables and figures will be provided for endpoints as described in the following sections. Response rate endpoints will be summarized by providing the point and interval estimates. Time-to-event variables will be summarized using Kaplan-Meier estimates and plots.

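### The Expansion Phase interim safety analysis counts only patients who complete 3 cycles, so it comes later when early stopping is more frequent

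*Protocol*

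**What the plan says.** Protocol 9.9 sets the Expansion look as follows: "In the Expansion Phase, an interim safety analysis will be conducted after a total of 20 patients complete 3 cycles of therapy". SAP 8.11 agrees: "An interim safety analysis will be conducted after a total of 20 patients complete 3 cycles of therapy in the Expansion Phase". The synopsis has the same trigger. None of the three places counts patients who stop early, gives a calendar or enrolment fallback, or says whether accrual pauses.

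For Segment 2, the preceding paragraph of 9.9 is worded differently: "after all patients complete 3 cycles of treatment or discontinue treatment, the data will be unblinded". Protocol 5.4.2 has the same Segment 2 rule.

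On size and pace, Protocol 9.4.2 says "Approximately 40 patients will be enrolled in the Expansion Phase" and Protocol 1.5.1 says "The expansion cohorts will be enrolled in parallel". Under Appendix A, "a cycle of therapy is considered to be 28 days with no rest periods in between cycles", so 3 cycles take 84 days.

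There are two other safeguards. Protocol 9.8 and SAP 8.11 require DRC review of safety, PK and PD data at least every 6 months in Expansion. They also close a dose to further enrolment if its DLT rate goes above 33% at any time.

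**The concern.** The trigger depends on the outcome it is meant to monitor. Each patient who leaves before day 84 must be replaced by a later one before the count reaches 20. The more often the regimen is stopped for toxicity or progression, the later the analysis.

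Some early stopping is foreseeable. Progression normally ends treatment (Protocol 4.4.1), and the first on-study scan is at week 8, before the 12-week completion point. ARant-Resistant patients, half of the phase, have already progressed on enzalutamide or a similar agent. If they stop CORT125281 they also stop enzalutamide (Protocol 5.7.1.1), so they cannot reach the count that way.

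At stake is whether the look comes while enrolment can still be changed.

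**Working it through.** **Inputs from the documents.** 20 completers required; about 40 patients (20 + 20), enrolled in parallel; 3 × 28 = 84 days = 12 weeks = 84/30.4375 = 2.76 months.

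**Inputs assumed, because the documents do not give them.** Completion probability *p*, from 0.4 to 0.9; accrual *m*, from 2 to 6 patients per month. The nearest planning figure is Segment 2's 16 DLT-evaluable of 20 enrolled (80%). It is not a completion rate, since patients with a DLT also count as evaluable.

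**The plan's own figure.** The documents do not say when the look falls. The 40 patients come from the power statements, which reproduce with exact binomial calculations:
- Abi-Resistant: at least 8 of 20, 23.5% against 47%: alpha 0.075, power 0.802.
- ARant-Resistant: at least 4 of 20, 8% against 26%: alpha 0.071, power 0.804.

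**Step 1: which patient is the 20th completer, and when.** On average it is patient 20/*p*, so the look falls at about 20/(*p·m*) + 2.76 months. All 40 are enrolled first if *m* exceeds (40 − 20/*p*)/2.76.

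| *p* | 20/*p* | Accrual above which all 40 are enrolled first | Time of look at 4/month |
|---|---|---|---|
| 0.9 | 22.2 | 6.4/month | 8.3 months |
| 0.8 | 25.0 | 5.4/month | 9.0 months |
| 0.7 | 28.6 | 4.1/month | 9.9 months |
| 0.6 | 33.3 | 2.4/month | 11.1 months |

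At 4/month, enrolment of 40 takes about 40/4 = 10 months.

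**Step 2: chance that the look comes only after all 40 are enrolled.** Simulation with Poisson accrual, 20,000 runs per setting:

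| *p* | 2/month | 4/month | 6/month |
|---|---|---|---|
| 0.9 | 0% | 5% | 43% |
| 0.8 | 1% | 20% | 66% |
| 0.7 | 10% | 48% | 85% |
| 0.6 | 36% | 73% | 89% |

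**Step 3: chance that the look never occurs.** This is P(Bin(40, *p*) ≤ 19): below 0.01% at *p* = 0.8, 0.2% at 0.7, 1.7% at 0.65, 7.4% at 0.6, 44% at 0.5 and 87% at 0.4.

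**Step 4: the amended trigger.** If the first 20 treated patients count once they complete or discontinue, the look falls at about 20/*m* + 2.76 months at the latest, whatever *p* is. At 4/month that is 5 + 2.76 = 7.8 months, earlier than Step 1 by 1.2 months (*p* = 0.8) to 2.1 months (*p* = 0.7).
- Enrolled by then, 20 + 2.76*m*: about 26, 31 and 37 at 2, 4 and 6 per month.
- Chance that all 40 are already enrolled, P(Poisson(2.76*m*) ≥ 20): about 1% at 4/month and 23% at 6/month.
- Break-even accrual: (40 − 20)/12 = 1.67 per week, or 7.2 per month.

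These times assume no cycle is delayed; Protocol 5.7 allows delays for toxicity. Time runs from Cycle 1 Day 1, because Food-Effect patients take a single dose 7 days earlier.

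**The case against.** **Other safeguards exist.** The 33% DLT rule applies at any time, is the only stated rule that stops Expansion enrolment, and does not wait for this look. The DRC review runs by the calendar and cannot be delayed by dropouts. If 6 months is counted from the start of Expansion, it precedes even the amended trigger when accrual is below 20/(26 − 12) = 1.43 per week. Both points stand, so a reader who infers that this is the only scheduled safety look would be wrong. The DLT rule is incomplete, however. Protocol 5.5 defines DLT-evaluation periods only for Segments 1 and 2, and Protocol 9.2 and SAP 6.3 limit the DLT-Evaluable Population to Dose-Determination cohorts.

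**The look may never happen.** A reader might infer this by extrapolating from Segment 1, where "One patient was not evaluable for DLTs due to disease progression during Cycle 1" (1 of 12 treated, or 1 of 7 in Cohort 3). The documents do not support it. It rests on one patient, on twice-daily fasting dosing rather than the fed Expansion regimen, and the exact 95% interval for 1/12 is about 0.2% to 38%. Being non-evaluable for DLTs is also not the same as being off therapy (Protocol 5.4.1).

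**Some early stoppers may count.** Study treatment is defined as either drug or both (Protocol 5). Abi-Resistant patients who stop CORT125281 may stay on enzalutamide (5.7.1.1) and could be read as completing 3 cycles of therapy. This stands as an ambiguity in the trigger, so it would be too strong to say that no patient stopping CORT125281 can count.

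**The wording may be shorthand.** Protocol 9.8, the synopsis and SAP 8.11 also describe the Segment 2 review by completion alone, although 5.4.2 and 9.9 include discontinuers. That is possible, but nothing in the Expansion text says so.

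**Full exposure is a legitimate aim.** Requiring 20 patients with 84 days of exposure is defensible, but the plan does not give this as its reason.

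**Conclusion.** The concern holds, at modest size. As written, early stops do not advance the look, and it comes later when they are more frequent. At an assumed 4 patients per month and 70–80% completion, it comes only after full enrolment in about 20–48% of cases, against about 1% with the amended trigger. At 2 per month the range is 1–10%. Failure to occur at all is a practical risk only at about 60% completion or less, and no figure in the documents points there.

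The result rests on assumed accrual and completion, on no pause in enrolment, and on reading the trigger as completers of CORT125281. The DRC review and the DLT rule reduce the consequence without removing it. This is a cheap improvement, not a failure of safety oversight.

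**What to change.** In the synopsis, Protocol 9.9 and SAP 8.11, change the trigger to: *after the first 20 treated Expansion Phase patients have completed 3 cycles or discontinued CORT125281*. This follows the Segment 2 rule, and naming CORT125281 settles how to count patients who continue on enzalutamide alone. Without cycle delays, the look then falls no later than 84 days after the 20th patient's Cycle 1 Day 1, and it cannot fail to occur once 20 are treated.

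The cost is one phrase in three places and slightly less cumulative exposure at the look. Above about 1.67 patients per week the amended look would still follow full enrolment, so the plan should also say whether enrolment continues while the review is pending. Separately, the any-time DLT rule needs a stated evaluation window and denominator for Expansion.
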